7. RATIONALE AND BACKGROUND

In terms of chronic obstructive pulmonary disease (COPD) drug therapy, the current German COPD guideline (S2) [1] recommends a treatment escalation procedure (Figure 1). For incident COPD patients (for the sake of simplicity, newly diagnosed and so far treatment naïve COPD patients will be referred to as “incident COPD patients” in the following), the guideline recommends the following:

- No treatment (low symptom burden) or
- Short-acting beta antagonist (SABA) or short-acting muscarinic antagonist (SAMA) or
- Long-acting beta agonist (LABA) or long-acting muscarinic antagonist (LAMA) or LABA+LAMA.

All other treatments, particularly combination treatments including inhaled corticosteroids (ICS), are only recommended as escalation therapy. However, despite the increasing evidence (e.g. WISDOM study [3], FLAME study [4]), there might exist the view that early use of ICS in the treatment of COPD might be advisable, and might be prescribed in a substantial percentage of COPD-incident patients.

Figure 1 Treatment recommendations with regard to COPD stages, according to German 2018 S2 guideline [1]

Medikamentöse Dauertherapie der COPD	
Symptome - Ausmaß der Lungenfunktions-einschränkungen berücksichtigen	Medikamentöse Therapie
Wenig (z. B. CAT < 10) GOLD Gruppe A	- Keine - SABA + SAMA (initial) - LABA oder LAMA
Viel (z. B. CAT \geq 10) GOLD Gruppe B	- LABA oder LAMA - LABA + LAMA
Exazerbationen > 1 oder Exazerbation mit Hospitalisierung GOLD Gruppen C und D	
Nicht vorbehandelt	LAMA oder LAMA + LABA
Vorbehandelt	LAMA + LABA
Eskalation/Wechsel	 LABA + ICS → LAMA + LABA + ICS
	\pm Roflumilast (Phänotyp chronische Bronchitis)

Currently, knowledge on real world treatment of incident COPD patients in Germany is sparse, in particular regarding the frequency of different drug therapy prescriptions and the frequency of early therapy escalation including ICS. With the current analyses, we aim to emphasize the central role of LAMA/LABA therapy in COPD and importance of treatment guideline adherence.

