¹³ Even if this study is based on fixed follow-up periods, death of some patients during the follow-up period might lead to shorter follow-up periods than 12, 24, or 36 months in some patients. That is why above numbers will be reported per observed patient year.

¹⁴ Analyses will be done for all three defined follow-up periods (12 months, 24 months, 36 months). For major treatment patterns, characteristics of respective patients will be described.

¹⁵ Switching between different drugs of the same drug class (LAMA,LABA,ICS) will not be taken into account for this analysis.

Table 2 (cont'd)

Description of treatment patterns/cascades (template for reported outcomes)
 (please note: below table might not show all theoretically possible treatment patterns. In the analysis, based on observed treatment patterns, all treatment pattern combinations that were observed in >5% of the patient population will be reported)

Therapy pattern after index date	1st line	2nd line	3rd line	4th line	N (%) of patients
Mono, with switch to dual therapy	LAMA	LAMA+LABA	-	-	...
		LAMA+ICS			
		LABA+ICS			
	LABA	LAMA+LABA		-	
		LAMA+ICS			
		LABA+ ICS			
Mono, with switch to dual therapy and subsequent switch to another dual therapy	LAMA	LAMA+LABA	LAMA+ICS		
		LAMA+ICS	LAMA+LABA		
		LABA+ICS	LABA+ICS		
	LABA	LABA+LAMA	LABA+ICS		
		LABA+ ICS	LABA+LAMA		
		LAMA+ICS	LAMA+ICS		
Mono, with switch to dual therapy and subsequent triple therapy	LAMA	LAMA+LABA	LAMA+LABA+ICS	-	...
		LAMA+ICS	LAMA+LABA+ICS		
	LABA	LAMA+LABA	LAMA+LABA+ICS	-	
		LABA+ ICS	LAMA+LABA+ICS		
Mono, with switch to triple therapy	LAMA	LAMA+LABA+ICS			
	LABA	LAMA+LABA+ICS			

Table 2 (cont'd)

Description of treatment patterns/cascades (template for reported outcomes)
 (please note: below table might not show all theoretically possible treatment patterns. In the analysis, based on observed treatment patterns, all treatment pattern combinations that were observed in >5% of the patient population will be reported)

Therapy pattern after index date	1st line	2nd line	3rd line	4th line	N (%) of patients
Dual therapy, no switch during follow-up period	LAMA+LABA LABA+ICS LAMA+ICS	- - -	- - -	- - -	...
Dual therapy with switch to another dual therapy	LAMA+LABA LAMA+ICS LABA+ICS	LAMA+ICS LAMA+LABA LAMA+ICS	LAMA+LABA LAMA+ICS		
Dual therapy with switch to triple therapy	LAMA+LABA LAMA+ICS LABA+ICS	LAMA+LABA+ ICS LAMA+LABA+ ICS LAMA+LABA+ ICS	-		
Triple therapy, no switch during follow-up period	LAMA+LABA+ICS				

Table 2 (cont'd)

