9.3.2.2 Secondary outcomes

First Secondary

Comparison of initial drug treatment with treatment guidelines

Comparison of real-world treatment of patients with guidelines will be done based on two samples: COPD-12 and COPD DMP-12. Assessment will generally be done for two time points:

- For all patients at index date (+ 4 weeks)
- For patients who received a triple combination (LABA+LAMA+ICS) at first day of triple therapy prescription.

Prescription patterns will be compared with German treatment guideline recommendations. Here, the 2018 S2 guideline [1] will be used (sensitivity analysis: 2012 guideline, which is an updated version of the 2006 guideline [2]). Obviously, as patients are only observed until mid of 2018, it cannot be expected that they were treated in line with the 2018 S2 guideline. However, this analysis describes potential needs to adapt the current treatment of the patients in the future, and is as such important for preparation of later initiatives to optimize the treatment of the patients.

Based on claims data only, assessment of the severity of the COPD disease for COPD patients is hardly possible. The reason is that neither FEV₁ data nor symptoms' data as measured by the COPD assessment test (CAT) or the Modified Medical Research Council (mMRC) are available in a claims dataset. So, for the comparison of the real-world treatment with 2018/2012 guideline recommendations, based on sample COPD-12, the following analyses will be done:

- COPD-12, at index date
 - Based on the inclusion criteria, an incident COPD patient did not experience any exacerbation in the previous 12 months, as no such diagnosis was documented. So, the initial treatment with long-acting bronchodilators should generally not include use of ICS (both guidelines). Moreover, based on the 2012 guideline, a therapy with long-acting bronchodilators should start with either a LAMA or a LABA, but not with a combination of them.

So, based on these criteria, the following percentages will be reported:

- Percentage of patients not treated in line with 2018 guideline
 - Therapy at index date includes ICS
- Percentage of patients not treated in line with 2012 guideline
 - Therapy at index date includes ICS or a LABA/LAMA combination or triple therapy of LABA+LAMA+ICS¹⁶
- COPD-12, at first date of an observed LABA+LAMA+ICS combination, which is not the index date

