 - According to both guidelines mentioned above, a triple combination treatment LABA+LAMA+ICS should only be prescribed if a patient experienced at least two exacerbations or one severe exacerbation requiring an inpatient treatment in the history of the disease. Based on this, the following percentage will be reported:
 - Percentage of patients not treated in line with the 2012/2018 guideline
 - Only 1 or less confirmed outpatient diagnoses and no inpatient diagnosis of a COPD exacerbation (ICD-10 J44.1) before date of prescription of a triple therapy.
- COPD-12, for the whole follow-up period (12 months)
 - A treatment intensification (mono to dual therapy, mono to triple or dual to triple therapy) should generally be accompanied by a thorough application of recommended diagnostic measures, according to the 2012/2018 guidelines. For these, typically, general practitioners (GPs) do not have the necessary infrastructure. Based on this, the following percentage will be reported:
 - Percentage of patients who received a treatment intensification without any previous visit of a pneumologist or hospital (same quarter or previous quarter)

Sensitivity analysis

In a first sensitivity analysis, those of above patients will be included for whom at least one ICD-10 COPD code that provides information up to the 5th level is documented: These subcodes include information about FEV₁ level. For patients for whom such a subcode is available, in this analysis, disease severity will be defined based on this information, which is mainly important when applying the 2012 guideline.

¹⁶ Of those patients starting with triple therapy of LABA+LAMA+ICS at time of incident COPD diagnosis, physician visits (separately of cardiologists, pneumologists) and measures of lung function (DMP-dataset only) before or at index date will be reported. Time since last physician visits to a cardiologist or a pneumologist will be reported too.

In a second sensitivity analysis, the sample COPD DMP-12 will be analyzed. In the DMP data set, additional documentation about exacerbation history and FEV₁ is available. Based on these data, the following analyses are planned:

- COPD DMP-12, at index date: no additional analysis, as DMP data will not be available for the pre-index period
- COPD DMP-12, at first date of an observed LABA+LAMA+ICS combination, which is not the index date; patients for whom at least one DMP entry before date of prescription of above combination will be included

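### For the 2018 guideline, the triple-therapy adherence rule ignores earlier treatment, so some untreated patients who go straight to triple count as in line despite the plan's own Figure 1

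*Combined protocol and SAP*

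**What the plan says.** Section 9.3.2.2 (First Secondary) assesses COPD-12 patients "at first date of an observed LABA+LAMA+ICS combination, which is not the index date". The premise, attributed to both guidelines, is that "a triple combination treatment LABA+LAMA+ICS should only be prescribed if a patient experienced at least two exacerbations or one severe exacerbation requiring" inpatient treatment. A patient is scored not in line if the record shows: "Only 1 or less confirmed outpatient diagnoses and no inpatient diagnosis of a COPD exacerbation (ICD-10 J44.1) before date of prescription of a triple therapy". One pooled 2012/2018 percentage is reported.

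The second sensitivity analysis repeats this condition for COPD DMP-12 under 2018. Under 2012 it adds exacerbations documented in the DMP data and FEV₁ below 50%. None of these versions looks at what the patient took before triple therapy.

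Section 7 describes the 2018 guideline differently. In Figure 1, patients with more than one exacerbation, or a hospitalised one, are split by prior treatment. The row for those not pre-treated reads "LAMA oder LAMA + LABA". Triple therapy appears only in the escalation/switch row, as "LABA + ICS → LAMA + LABA + ICS". The text above the figure says that ICS combinations "are only recommended as escalation therapy".

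A separate criterion applies early. Section 9.3.2.2 plans an assessment "For all patients at index date (+ 4 weeks", and any ICS at that point is not in line with 2018.

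**The concern.** Section 9.2 admits only patients with no COPD medication (Suppl. Table 2) in the 12 months before index. Whether a patient had earlier long-acting treatment is therefore fully observable, and it is the element on which Figure 1 splits patients with a qualifying exacerbation history. The scoring rule drops that element.

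The rationale names early escalation including ICS as the gap the study should fill. A first long-acting regimen that is already triple is the clearest case of early escalation. The rule counts such a start as in line once the exacerbation threshold is met.

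The classification also has a further use. The first-secondary row of Table 4 compares patients treated in line and not in line, and fits a logistic regression for factors associated with guideline-conform treatment. Wherever status is taken from the triple rule, the same patients sit on the in-line side.

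**Working it through.** The plan states no figure on this point to reproduce. The check is a comparison of two classifiers, followed by a formula for the effect.

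**1. The two statements of the 2018 criterion**

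- Plan rule (Section 9.3.2.2): not in line if there is at most one outpatient and no inpatient J44.1 before triple; otherwise in line.
- Figure 1 (Section 7), read as: in line if the same exacerbation threshold is met and some long-acting treatment came before triple. That any earlier long-acting regimen suffices is an assumption.

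Each cell gives plan rule / Figure 1 reading.

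| Regimen before first triple | No J44.1 | 1 outpatient | 2 outpatient | 1 inpatient |
|---|---|---|---|---|
| none | not / not | not / not | **in / not** | **in / not** |
| mono | not / not | not / not | in / in | in / in |
| LAMA+LABA | not / not | not / not | in / in | in / in |
| LABA+ICS | not / not | not / not | in / in | in / in |

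The two disagree in 2 of 16 cells, both with no earlier long-acting treatment and a qualifying history. All 12 cells with earlier treatment agree.

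**2. Whether another measure catches these patients, by date of the none-to-triple start**

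This takes the 4-week window as applying to the index-date ICS criterion.

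- Index date: the triple rule does not apply; the ICS criterion scores not in line.
- Days 1 to 28: the ICS criterion scores not in line. The triple rule excludes only the index date itself, so it scores in line if the history qualifies. The same prescription gets two verdicts.
- After day 28: the ICS criterion no longer applies, and the triple rule scores in line if the history qualifies. The intensification check lists only steps from mono or dual therapy and tests only for a pneumologist or hospital visit. Nothing flags the patient.

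An example follows from the entry criteria. A patient enters through a hospital admission coded J44.1 and fills a first outpatient prescription, triple, on day 40. There is one inpatient J44.1 before a non-index triple date, so the patient is in line.

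**3. Size**

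Let p be the share of post-index triple starters not in line under the plan's rule, and s the share of the remaining starters who had no earlier long-acting treatment. With prior treatment also tested, the percentage becomes

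p′ = p + (1 − p) × s.

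The documents give neither p nor s. For assumed values:

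| p | s = 5% | s = 10% | s = 20% | s = 40% |
|---|---|---|---|---|
| 30% | 33.5% | 37% | 44% | 58% |
| 50% | 52.5% | 55% | 60% | 70% |
| 70% | 71.5% | 73% | 76% | 82% |

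The understatement (1 − p) × s runs from 0.30 × 0.05 = 1.5 points to 0.70 × 0.40 = 28 points. This range reflects the assumed inputs only. It includes starts on days 1 to 28, which the index-date criterion already flags, so the part that no measure catches is smaller.

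**The case against.** The strongest reply is that the rule is incomplete rather than contradictory. It states a necessary condition, and its threshold (at least two exacerbations, or one leading to hospital) matches the Figure 1 heading for these patients. That is fair as far as the published premise goes. However, Table 4 treats everyone who passes as treated in line, so in practice the necessary condition is used as a sufficient one.

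A reader might infer more than the documents support on four counts:

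- **That every jump from no treatment to triple after an exacerbation is scored in line.** It is not. A single outpatient J44.1 still gives not in line, and ICS starts within index date + 4 weeks are flagged separately. A footnote also adds reporting of physician visits and lung function for patients who start triple at diagnosis.
- **That the 2012 score is wrong in the same way.** Figure 1 shows 2018 only. For 2012 the plan gives only its own paraphrase, and the DMP-12 rule for 2012 also uses FEV₁.
- **That the path is common or the error large.** No document figure supports either.
- **That Figure 1 settles which earlier regimen is enough.** It can be read more strictly, with LAMA+LABA or LABA+ICS expected before triple. Mono-to-triple would then also depart from it.

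The need is also partly met. Table 2 includes "Mono, with switch to triple therapy" and first-line triple, and a Kaplan-Meier analysis covers time to triple. Neither is crossed with exacerbation history or adherence status, so the gap remains, although it is small to close.

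**Conclusion.** The point holds for the 2018 guideline, for the rule at the first non-index triple date in COPD-12 and its repeat in COPD DMP-12. Patients with no earlier long-acting treatment who start triple after at least one inpatient or at least two outpatient J44.1 diagnoses are counted as in line, whereas Figure 1 lists no triple therapy for them. Starts in the first four weeks can receive opposite classifications from the two measures; later starts are caught by no adherence measure.

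The error has one direction: relative to the plan's own figure, the 2018 percentage not in line can only be too low. Its size cannot be derived from the documents. The conclusion rests on the row structure of Figure 1 as it appears in the text and on reading the escalation/switch row as requiring some earlier treatment. It carries into the Table 4 comparisons and regression to the extent that the triple rule defines status there, which Table 4 does not spell out. No view is taken on which clinical criterion is right.

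**What to change.** - Reconcile the index-date criterion and both triple-date rules in Section 9.3.2.2 with Figure 1 and the Section 7 text. State whether prior treatment is part of the 2018 criterion, and how a triple start on days 1 to 28 is classified.
- Report the 2018 percentage separately from 2012 in COPD-12 in place of one pooled figure.
- Cross-tabulate triple starters by regimen before the first triple date (none, mono, LAMA+LABA, LABA+ICS, LAMA+ICS) and by qualifying exacerbation history. This makes none-to-triple starts visible and leaves the reader free to apply a looser or stricter reading of Figure 1.
- State in Table 4 which adherence status enters the comparisons and the regression, and how none-to-triple starts are coded there.

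The cost is one extra table from the line-of-therapy data already built for Table 2, plus a few sentences of definition. No new data are needed.

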 - According to both above guidelines, a triple combination treatment LABA+LAMA+ICS should only be prescribed if a patient experienced at least 2 exacerbations or one severe exacerbation requiring an inpatient treatment in the history of the disease. In addition, the 2012 guideline also recommended such a treatment in case a FEV₁<50% could be observed. Based on this, the following percentages will be reported:
 - Percentage of patients not treated in line with the 2018 guideline
 - Only one or no confirmed outpatient diagnosis and no inpatient diagnosis of a COPD exacerbation (ICD-10 J44.1) before date of prescription of a triple therapy.
 - Percentage of patients not treated in line with the 2012 guideline
 - Only one or no confirmed outpatient diagnosis and no inpatient diagnosis of a COPD exacerbation (ICD-10 J44.1) and only one or no outpatient diagnosis and no inpatient exacerbation diagnoses as documented in the DMP dataset and no documented FEV₁ value <50%.

Second Secondary

Description of exacerbation frequency

For all samples (COPD-12, COPD-24, COPD 36, COPD DMP-12, COPD DMP-24, COPD DMP-36, COPD-FULL DATA), exacerbation frequency in the pre-defined follow-up periods (12 months, 24 months, 36 months, patient-individual follow-up times) will be described. Because of the higher diagnosis validity, in the main analysis only severe exacerbations leading to an inpatient hospitalization (COPD exacerbation documented as main diagnosis: ICD-10 J44.1) will be considered. Moreover, in a separate analysis proxies will be used to estimate non-severe exacerbations. Therefore prescriptions of SCS/OCS either separately or in combination with antibiotics, will be considered as proxy for the treatment of a non-severe exacerbation (without an inpatient hospitalization). Exacerbation frequency (once for severe and once for non-severe exacerbations) will be reported as percentage of patients having experienced at least 1 exacerbation, exactly 1 exacerbation, exactly 2 exacerbations, exactly 3 exacerbations, and >3 exacerbations, and as mean number of exacerbations per observed patient-year.

Third Secondary

Description of health care resource use and direct treatment cost

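### The COPD-12 triple-therapy figure carries a combined 2012/2018 label but omits the FEV1 criterion that the plan itself attributes to the 2012 guideline, so for 2012 it is only an upper bound

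*Combined protocol and SAP*

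**What the plan says.** The relevant text is in section 9.3.2.2, under the first secondary outcome.

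- **COPD-12, first triple-therapy date other than the index date.** The plan sets a single condition for the three-drug regimen under both guidelines: it "should only be prescribed if a patient experienced at least two exacerbations or one severe exacerbation requiring an inpatient treatment in the history of the" (sentence cut here). It reports a single figure, "Percentage of patients not treated in line with the 2012/2018 guideline". The flagging rule is "Only 1 or less confirmed outpatient diagnoses and no inpatient diagnosis", where J44.1 codes count up to the date triple therapy is prescribed. There is no FEV1 term.
- **COPD DMP-12, same time point.** The plan repeats the exacerbation criterion for both guidelines and then adds: "In addition, the 2012 guideline also recommended such a treatment in case a FEV₁<50% could be observed". It reports a 2018 and a 2012 percentage separately. The 2012 rule ends with the condition "and no documented FEV₁ value <50" (per cent), so a low FEV1 alone takes a patient out of the non-adherent group.
- **First sensitivity analysis.** This is limited to patients for whom "at least one ICD-10 COPD code that provides information up to the 5th level is documented". The plan says these subcodes carry FEV1 information and matter mainly for the 2012 guideline. It gives no triple-therapy rule or cut-off for them and does not say when the code must be dated.
- **Context.** The 2018 guideline is the main reference and the 2012 comparison is called a sensitivity analysis. The plan explains that claims data contain no FEV1 values.

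**The concern.** The plan defines 2012 non-adherence at the start of triple therapy in two ways, and the larger sample gets the version without FEV1. The combined label is also out of step with the rest of the section: for COPD-12 at the index date, and for COPD DMP-12, the two guidelines get separate percentages.

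Comparison with both guideline versions is a stated objective (section 8). The plan concedes that patients observed only to mid-2018 cannot be expected to have followed the 2018 guideline, so readers are likely to take the 2012 label as the measure of actual non-adherence. Table 4 (section 9.7.1) also plans group comparisons and a logistic regression on adherence status. If this classification feeds them, patients with low FEV1 and few exacerbation codes enter the wrong 2012 group. Section 7 gives emphasis on LAMA/LABA therapy and guideline adherence as an aim, so an omission that can only raise non-adherence will attract criticism.

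**Working it through.** The plan states no expected percentage for this endpoint, so there is no figure to reproduce. The check compares the two rules and then works out what the difference implies.

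**1. Where the rules differ.** Take outpatient J44.1 diagnoses (0, 1, 2 or more), inpatient J44.1 (no, yes) and FEV1 below 50% (no, yes). That gives 3 x 2 x 2 = 12 states. Exacerbation ascertainment is held fixed at the claims codes.

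| Outpatient J44.1 | Inpatient J44.1 | FEV1 below 50% | COPD-12 combined rule | Same rule plus the FEV1 term |
|---|---|---|---|---|
| 0 | no | yes | not in line | in line |
| 1 | no | yes | not in line | in line |
| other 10 states | | | same result | same result |

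No state differs in the other direction. Omitting FEV1 can therefore only raise the 2012 percentage, and it does so as soon as one such patient exists. The 2018 figure is unaffected.

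**2. Size in general form.** Let M be the percentage flagged by the combined rule and f the share of flagged patients with FEV1 below 50%. Then:

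- 2012 percentage = M x (1 - f)
- overstatement factor = M / [M x (1 - f)] = 1/(1 - f)

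The factor does not depend on M. The documents give neither M nor f. The values below are assumptions, for illustration only.

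| f (assumed) | Factor 1/(1 - f) | 2012 percentage if M = 60% (assumed) |
|---|---|---|
| 0% | 1.00 | 60% |
| 10% | 1.11 | 54% |
| 20% | 1.25 | 48% |
| 30% | 1.43 | 42% |
| 50% | 2.00 | 30% |

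**3. Bounds when FEV1 is partly unknown.** Let N be all triple starters in the analysis. Split the flagged patients into F_low (FEV1 below 50%), F_high (50% or above) and F_unk (unknown).

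- Current figure = (F_low + F_high + F_unk)/N
- Lower bound for 2012 = F_high/N
- Upper bound for 2012 = (F_high + F_unk)/N

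Hypothetical counts: N = 100, with 60 flagged, of whom F_low = 10, F_high = 40 and F_unk = 10. The current figure is 60/100 = 60%. The bounds are 40/100 = 40% and 50/100 = 50%.

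**4. Why the denominator must stay whole.** Patients with a qualifying exacerbation history are in line under either rule whatever their FEV1. Suppose FEV1 is also known for 10 of the 40 unflagged patients, and the analysis is restricted to patients with known FEV1. The result is 40/(50 + 10) = 67%, above the uncorrected 60%, because 30 patients known to be in line were dropped.

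**The case against.** The strongest defence has three parts.

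**FEV1 is not in claims data, and the plan says so.** This explains why the COPD-12 rule has no FEV1 term. It does not support the premise that both guidelines share one criterion, or a 2012 label on a rule that omits part of the 2012 criterion. The plan's own remark that 5th-level codes carry FEV1 information also means that part of COPD-12 can be classified.

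**The sensitivity analyses cover it.** The DMP-12 analysis does separate the guidelines, applies the FEV1 term to 2012 and requires a DMP entry before the triple prescription. That is real mitigation, but in a subset: section 9.5 puts patients with any DMP documentation at about 30%. The DMP-12 rule for 2012 also adds DMP-documented exacerbations, which the 2018 rule does not, so the gap between the two DMP-12 percentages does not isolate the effect of FEV1. The 5th-level-code analysis is also a subset. Neither changes or relabels the main figure.

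**The 2012 comparison is itself only a sensitivity analysis.** This stands and limits the weight of the point. It does not make the label correct.

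Two stronger readings are tempting but unsupported. A reader might infer that the reported figure is too high on balance. The rule counts diagnosis records, so one episode recorded twice could make a patient look adherent, while uncoded exacerbations act the other way; the net direction of all errors is not determined. A reader might also infer that the first sensitivity analysis admits severity codes dated after triple therapy started. The plan is silent on timing, which is a gap and not a rule.

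**Conclusion.** The two parts of section 9.3.2.2 contradict each other on the 2012 criterion for triple therapy and must be reconciled. If the DMP-12 statement stands, the COPD-12 percentage is valid for 2018 only. For 2012 it is an upper bound with respect to the missing FEV1 criterion, overstated by a factor 1/(1-f). The direction follows from the plan's own rules, with exacerbation ascertainment held fixed. A reader might want a figure in percentage points, but the plan gives no FEV1 distribution among triple starters and no expected share without exacerbation codes, so none can be given. If instead the COPD-12 statement stands, the FEV1 term in the DMP-12 rule for 2012 is what needs correcting. This is worth changing before analysis. Its weight is moderate, because 2018 is the main reference and subset analyses are already planned.

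**What to change.** State the 2012 criterion once and use it in both samples. If the DMP-12 statement is kept:

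- Report 2018 and 2012 percentages separately for COPD-12. The existing rule serves for 2018.
- For 2012, keep all triple starters in the denominator and count those with a qualifying exacerbation history as in line whatever their FEV1.
- Split only the flagged patients into FEV1 below 50% (in line), 50% or above (not in line) and unknown. Use 5th-level codes or DMP values dated on or before the first triple prescription, and state how the subcodes map to the 50% cut-off.
- Report the 2012 percentage as a lower bound (unknown counted as in line) and an upper bound (unknown counted as not in line), with the number unknown.

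At minimum, label the existing COPD-12 figure an upper bound for 2012.

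The cost is a little more analysis (dating the severity information and adding table rows) and a range in place of a single 2012 figure. If few flagged patients have usable FEV1 information, the range will be wide, which reflects what the data can show. The fix uses only data sources already in the plan.
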